Neutrophil count	 normal  abnormal  unknown	If abnormal, specify test result:	If abnormal, date of test: _____
Lymphocyte count	 normal  abnormal  unknown	If abnormal, specify test result:	If abnormal, date of test: _____
Other, specify:	 normal  abnormal  unknown	If abnormal, specify test result:	If abnormal, date of test: _____

Table 8: Vaccinations administered to infant at birth and during first year of age

Vaccinations administered at birth and during first year of age	Date administered	Infant's age on day of vaccination	Comments (abnormal outcome, reason for postponing vaccination, etc.)
 Hepatitis B			
 Rotavirus			
 Diphtheria, tetanus, and pertussis			
 Hemophilus influenza type b			
 Pneumococcal			
 Poliovirus			
 Attenuated oral polio vaccine			
 Inactivated polio vaccine			
 Meningococcal group B bacteria			
 Tuberculosis (Bacille Calmette Guérin, BCG) bacteria			
 Other vaccination, specify:			

Table 9: Fetal/neonatal abnormalities in previous pregnancies

Fetal/neonatal abnormalities (in previous pregnancies)	Please, provide specifics including contributing factors
None  Yes  Unknown 	
Infection; if yes, specify	
Death in utero; if yes, specify reason	
Birth defects; if yes, specify	
Family history of birth defects; if yes, specify	
Small for gestational age at birth (or Intrauterine growth retardation)	
Premature delivery (before 37 weeks)	
Other; specify	

Detailed information on health-related findings in infant during first year of life

Please enter text in the free text box below.

Appendix 10

Neuro-QOL

Anxiety – Short Form

Please respond to each question or statement by marking one box per row.

In the past 7 days...		Never	Rarely	Sometimes	Often	Always
EDANX53	I felt uneasy.....	 1	 2	 3	 4	 5
EDANX46	I felt nervous.....	 1	 2	 3	 4	 5
EDANX48	Many situations made me worry.....	 1	 2	 3	 4	 5
EDANX41	My worries overwhelmed me.....	 1	 2	 3	 4	 5
EDANX54	I felt tense.....	 1	 2	 3	 4	 5
EDANX55	I had difficulty calming down.....	 1	 2	 3	 4	 5
EDANX18	I had sudden feelings of panic.....	 1	 2	 3	 4	 5
NQANX07	I felt nervous when my normal routine was disturbed.....	 1	 2	 3	 4	 5

©2008-2018 David Cella and the PROMIS Health Organization on behalf of the National Institute for Neurological Disorders and Stroke (NINDS). Used with permission.

Depression – Short Form

Please respond to each question or statement by marking one box per row.

In the past 7 days...		Never	Rarely	Sometimes	Often	Always
EDDEP29	I felt depressed.....	 1	 2	 3	 4	 5
EDDEP41	I felt hopeless.....	 1	 2	 3	 4	 5
EDDEP09	I felt that nothing could cheer me up.....	 1	 2	 3	 4	 5
EDDEP48	I felt that my life was empty.....	 1	 2	 3	 4	 5
EDDEP04	I felt worthless.....	 1	 2	 3	 4	 5
EDDEP36	I felt unhappy.....	 1	 2	 3	 4	 5
EDDEP39	I felt I had no reason for living.....	 1	 2	 3	 4	 5
EDDEP45	I felt that nothing was interesting.....	 1	 2	 3	 4	 5

Fatigue – Short Form

Please respond to each question or statement by marking one box per row.

In the past 7 days...		Never	Rarely	Sometimes	Often	Always
NQFTG13	I felt exhausted.....	 1	 2	 3	 4	 5
NQFTG11	I felt that I had no energy.....	 1	 2	 3	 4	 5
NQFTG15	I felt fatigued.....	 1	 2	 3	 4	 5
NQFTG06	I was too tired to do my household chores.	 1	 2	 3	 4	 5
NQFTG07	I was too tired to leave the house.....	 1	 2	 3	 4	 5
NQFTG10	I was frustrated by being too tired to do the things I wanted to do.....	 1	 2	 3	 4	 5
NQFTG14	I felt tired.....	 1	 2	 3	 4	 5
NQFTG02	I had to limit my social activity because I was tired.....	 1	 2	 3	 4	 5

Cognition Function– Short Form

Please respond to each question or statement by marking one box per row.

	In the past 7 days...					
		Never	Rarely (once)	Sometimes (2-3 times)	Often (once a day)	Very often (several times a day)
NQCOG64r1	I had to read something several times to understand it.....	 5	 4	 3	 2	 1
NQCOG75r1	My thinking was slow.....	 5	 4	 3	 2	 1
NQCOG77r1	I had to work really hard to pay attention or I would make a mistake.....	 5	 4	 3	 2	 1
NQCOG80r1	I had trouble concentrating.....	 5	 4	 3	 2	 1

How much DIFFICULTY do you currently have...

		None	A little	Somewhat	A lot	Cannot do
NQCOG22r1	reading and following complex instructions (e.g., directions for a new medication)?.....	 5	 4	 3	 2	 1
NQCOG24r1	planning for and keeping appointments that are not part of your weekly routine, (e.g., a therapy or doctor appointment, or a social gathering with friends and family)?.....	 5	 4	 3	 2	 1
NQCOG25r1	managing your time to do most of your daily activities?.....	 5	 4	 3	 2	 1
NQCOG40r1	learning new tasks or instructions?.....	 5	 4	 3	 2	 1

Emotional and Behavioral Dyscontrol – Short Form

Please respond to each question or statement by marking one box per row.

In the past 7 days...		Never	Rarely	Sometimes	Often	Always
EDANG42	I had trouble controlling my temper.....	 1	 2	 3	 4	 5
NQPER05	It was hard to control my behavior.....	 1	 2	 3	 4	 5
NQPER06	I said or did things without thinking.....	 1	 2	 3	 4	 5
NQPER07	I got impatient with other people.....	 1	 2	 3	 4	 5
NQPER11	I was irritable around other people.....	 1	 2	 3	 4	 5
NQPER12	I was bothered by little things.....	 1	 2	 3	 4	 5
NQPER17	I became easily upset.....	 1	 2	 3	 4	 5
NQPER19	I was in conflict with others.....	 1	 2	 3	 4	 5

Positive Affect and Well-Being - Short Form

Please respond to each question or statement by marking one box per row.

Lately...		Never	Rarely	Sometimes	Often	Always
NQPPF14	I had a sense of well-being.....	 1	 2	 3	 4	 5
NQPPF12	I felt hopeful.....	 1	 2	 3	 4	 5
NQPPF15	My life was satisfying.....	 1	 2	 3	 4	 5
NQPPF20	My life had purpose.....	 1	 2	 3	 4	 5
NQPPF17	My life had meaning.....	 1	 2	 3	 4	 5
NQPPF22	I felt cheerful.....	 1	 2	 3	 4	 5
NQPPF19	My life was worth living.....	 1	 2	 3	 4	 5
NQPPF16	I had a sense of balance in my life.....	 1	 2	 3	 4	 5
NQPPF07	Many areas of my life were interesting to me.....	 1	 2	 3	 4	 5

Ability to Participate in Social Roles and Activities – Short Form

Please respond to each question or statement by marking one box per row.

	In the past 7 days...	Never	Rarely	Sometimes	Often	Always
NQPRF01	I can keep up with my family responsibilities.....	 1	 2	 3	 4	 5
NQPRF03	I am able to do all of my regular family activities.....	 1	 2	 3	 4	 5
NQPRF08	I am able to socialize with my friends.....	 1	 2	 3	 4	 5
NQPRF09	I am able to do all of my regular activities with friends.....	 1	 2	 3	 4	 5
NQPRF17	I can keep up with my social commitments.....	 1	 2	 3	 4	 5
NQPRF26	I am able to participate in leisure activities.....	 1	 2	 3	 4	 5
NQPRF32	I am able to perform my daily routines.....	 1	 2	 3	 4	 5
NQPRF34	I can keep up with my work responsibilities (include work at home)....	 1	 2	 3	 4	 5

Satisfaction with Social Roles and Activities – Short Form

Please respond to each question or statement by marking one box per row.

In the past 7 days...		Not at all	A little bit	Somewhat	Quite a bit	Very much
NQSAT 03	I am bothered by my limitations in regular family activities	 5	 4	 3	 2	 1
NQSAT 23	I am disappointed in my ability to socialize with my family.....	 5	 4	 3	 2	 1
NQSAT14	I am bothered by limitations in my regular activities with friends.....	 5	 4	 3	 2	 1
NQSAT11	I am disappointed in my ability to meet the needs of my friends	 5	 4	 3	 2	 1

In the past 7 days...		Not at all	A little bit	Somewhat	Quite a bit	Very much
NQSAT33	I am satisfied with my ability to do things for fun outside my home.....	 1	 2	 3	 4	 5
NQSAT32	I am satisfied with the amount of time I spend doing leisure activities.....	 1	 2	 3	 4	 5
NQSAT47	I am satisfied with how much of my work I can do (include work at home).....	 1	 2	 3	 4	 5
NQSAT 46	I am satisfied with my ability to do household chores or tasks.....	 1	 2	 3	 4	 5

Communication – Short Form

Please respond to each question or statement by marking one box per row.

How much DIFFICULTY do you currently have...

None		A little	Somewhat	A lot	Cannot do	
NQCOG01	writing notes to yourself, such as appointments or 'to do' lists?.....	 5	 4	 3	 2	 1
NQCOG04	understanding family and friends on the phone?.....	 5	 4	 3	 2	 1
NQCOG08	carrying on a conversation with a small group of familiar people (e.g., family or a few friends)?.....	 5	 4	 3	 2	 1
NQCOG10	organizing what you want to say?.....	 5	 4	 3	 2	 1
NQCOG11	speaking clearly enough to use the telephone?.....	 5	 4	 3	 2	 1

Upper Extremity Function (Fine Motor, ADL) – Short Form

Please respond to each question or statement by marking one box per row.

		Without any difficulty	With a little difficulty	With some difficulty	With much difficulty	Unable to do
PFA40	Are you able to turn a key in a lock?.....	 5	 4	 3	 2	 1
PFA50	Are you able to brush your teeth?	 5	 4	 3	 2	 1
NQUEX44	Are you able to make a phone call using a touch tone key-pad?	 5	 4	 3	 2	 1
PFB21	Are you able to pick up coins from a table top?	 5	 4	 3	 2	 1
PFA43	Are you able to write with a pen or pencil?	 5	 4	 3	 2	 1
PFA35	Are you able to open and close a zipper?...	 5	 4	 3	 2	 1
PFA55	Are you able to wash and dry your body?..	 5	 4	 3	 2	 1
PFB26	Are you able to shampoo your hair?	 5	 4	 3	 2	 1

Lower Extremity Function (Mobility) – Short Form

Please respond to each question or statement by marking one box per row.

		Without any difficulty	With a little difficulty	With some difficulty	With much difficulty	Unable to do
PFC45	Are you able to get on and off the toilet? ...	 5	 4	 3	 2	 1
PFA30	Are you able to step up and down curbs?...	 5	 4	 3	 2	 1
PFA56	Are you able to get in and out of a car?	 5	 4	 3	 2	 1
PFA45	Are you able to get out of bed into a chair?	 5	 4	 3	 2	 1
PFA12	Are you able to push open a heavy door? ..	 5	 4	 3	 2	 1
PFA53	Are you able to run errands and shop?	 5	 4	 3	 2	 1
PFA31	Are you able to get up off the floor from lying on your back without help?	 5	 4	 3	 2	 1
PFA23	Are you able to go for a walk of at least 15 minutes?	 5	 4	 3	 2	 1

Sleep Disturbance – Short Form

Please respond to each question or statement by marking one box per row.

In the past 7 days...		Never	Rarely	Sometimes	Often	Always
NQSLP02	I had to force myself to get up in the morning.....	 1	 2	 3	 4	 5
NQSLP03	I had trouble stopping my thoughts at bedtime.....	 1	 2	 3	 4	 5
NQSLP04	I was sleepy during the daytime.....	 1	 2	 3	 4	 5
NQSLP05	I had trouble sleeping because of bad dreams.....	 1	 2	 3	 4	 5
NQSLP07	I had trouble falling asleep.....	 1	 2	 3	 4	 5
NQSLP12	Pain woke me up.....	 1	 2	 3	 4	 5
NQSLP13	I avoided or cancelled activities with my friends because I was tired from having a bad night's sleep.....	 1	 2	 3	 4	 5
NQSLP18	I felt physically tense during the middle of the night or early morning hours.....	 1	 2	 3	 4	 5

©2008-2013 David Cella and the PROMIS Health Organization on behalf of the National Institute for Neurological Disorders and Stroke (NINDS). Used with permission.

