For this study, a neurologic event consistent with CNS demyelination is defined as the occurrence of new and/or worsening neurological symptoms suggestive of MS. Symptoms must persist for >24 hours and should not be attributable to confounding clinical factors (e.g., fever, infection, injury, adverse reactions to medications) and be immediately preceded by a stable or improving neurological state for least 30 days. The new or worsening neurological symptoms must be adjudicated by a Sponsor-appointed adjudication committee, comprised of three expert neuroimmunology clinicians, who will review documentation associated with the event and confirm whether a relapse has occurred. Confirmed relapses will contribute to the primary endpoint.

Investigators will also screen patients for signs and symptoms of worsening neurological function localized to the cerebral cortex, such as cortical symptoms/signs, behavioral and neuropsychological alteration, retrochiasmal visual defects, hemiparesis, and cerebellar symptoms/signs (e.g., gait abnormalities, limb incoordination). Patients with

suspected PML should be withheld from ocrelizumab treatment until PML is ruled out by complete clinical evaluation and appropriate diagnostic testing (see Appendix 7). A patient with confirmed PML should be withdrawn from the study. PML should be reported as a serious adverse event (with all available information) with immediate notification of the Medical Monitor.

If an investigator determines that further testing (e.g. MRI) is necessary to evaluate a neurologic event, this would be performed according to standard of medical care. Results from any clinically warranted MRIs will be recorded in the eCRF.

Clinical neurologic events (i.e., regardless of whether they meet criteria for a protocol-defined neurologic event) will be recorded in the eCRF.

Laboratory, Biomarker, and Other Biological Samples

Samples for the laboratory tests will be collected on the days indicated in the schedule of activities (see Appendix 1).

Pre-infusion laboratory test results need to be available for review before each infusion, unless otherwise specified.

Samples for the following laboratory tests will be sent to the sites' local laboratory for analysis according to the appropriate SOA unless otherwise indicated (further details will be provided in the laboratory manual).

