When a patient withdraws from the study, samples collected prior to the date of withdrawal may still be analyzed, unless the patient specifically requests that the samples be destroyed or local laws require destruction of the samples. However, if samples have been tested prior to withdrawal, results from those tests will remain as part of the overall research data.

Data arising from sample analysis will be subject to the confidentiality standards described in Section 4.5.19.2 and Section 8.4.

Hepatitis Screening and Liver Function Monitoring

Patients with recurrent or chronic hepatitis B or history/presence of hepatitis C infection must be excluded from enrollment into the study. Hepatitis B and C serology will be performed at screening.

A positive result to either HBsAg, total HBcAb associated with positive viral DNA titers as measured by PCR, or a positive result for HepCAb should result in the patient's exclusion.

Patients with evidence of past resolved hepatitis B infection (i.e., positive total HBcAb associated with a negative viral DNA) can be enrolled and will have the hepatitis B viral DNA checked regularly as per the schedule of activities (see Appendix 1).

Patients in whom the viral DNA becomes positive but in whom the quantity is at the lower limit of detection of the assay should have the test repeated as soon as possible. Patients found to have a confirmed viral DNA-positive test should be referred to a hepatologist for immediate assessment. These patients will not receive further ocrelizumab infusions.

Liver function (i.e., ALT, AST, alkaline phosphatase, and total bilirubin) should be reviewed throughout the study. Patients developing evidence of liver dysfunction should be assessed and, if necessary, referred to a hepatologist or other appropriately qualified expert. Study drug should be withheld until the diagnosis of viral hepatitis has been excluded.

Patients developing hepatitis B or C should be withdrawn from the study. Should treatment be prescribed, this will be recorded on the eCRF. Patients with viral hepatitis due to other agents, such as hepatitis A, may resume treatment after the patient's recovery.

Patient-Reported Outcomes

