Based on additional patient exposure an association between decrease in immunoglobulins and serious infections with ocrelizumab treatment was observed and was most apparent for IgG. There was no difference in the pattern (type, latency, duration, outcome) of the serious infections reported in this subset of patients compared to the overall serious infections profile. In addition, risk factors for a subset of patients at higher risk of serious infections could not be identified.

Delayed Return of Peripheral B Cells

Treatment with ocrelizumab leads to rapid depletion of CD19+ B cells in blood by 14 days posttreatment (first timepoint of assessment) as an expected pharmacologic

effect. This was sustained throughout the treatment period. The longest follow-up duration after the last ocrelizumab infusion from Phase II Study WA21493 in 51 patients indicates that the median time to repletion (returned to baseline/LLN, whichever occurred first) of B cells was 72 weeks (range 27–175 weeks). Patients with prolonged B-cell depletion should be monitored until his or her B cells have repleted.

Potential Risks

Progressive Multifocal Leukoencephalopathy

It has been reported in patients receiving ocrelizumab but only in patients where other contributory factors were present, such as prior immunosuppressive treatment (for example natalizumab or fingolimod). Physicians should be vigilant for early signs and symptoms of PML, which can include any new onset, or worsening of neurological signs or symptoms as these can be similar to an MS relapse. If PML is suspected, dosing with ocrelizumab must be withheld. Evaluation of PML, including MRI, confirmatory CSF testing for JC Viral DNA and repeat neurological assessments, should be considered. If PML is confirmed, ocrelizumab must be discontinued permanently.

Refer to Appendix 7 for guidance for diagnosis of PML. Please see the Ocrelizumab Investigator's Brochure for more details.

Hypersensitivity Reactions

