AESIs are a subset of Events to Monitor (EtMs) of scientific and medical concern specific to the product, for which ongoing monitoring and rapid communication by the Investigator to the Sponsor is required. Such an event might require further investigation in order to characterize and understand it. Depending on the nature of the event, rapid communication by the trial Sponsor to other parties (e.g., Regulatory Authorities) may also be warranted.

Adverse events of special interest for this study include the following:

Cases of potential drug-induced liver injury that include an elevated ALT or AST in combination with either an elevated bilirubin or clinical jaundice, as defined by Hy's law:

Treatment-emergent ALT or AST $> 3 \times$ ULN in combination with total bilirubin $> 2 \times$ ULN

Treatment-emergent ALT or AST $> 3 \times$ ULN in combination with clinical jaundice

Data related to a suspected transmission of an infectious agent by the study drug (STIAMP), as defined below:

Any organism, virus, or infectious particle (e.g., prion protein transmitting transmissible spongiform encephalopathy), pathogenic or non-pathogenic, is considered an infectious agent. A transmission of an infectious agent may be suspected from clinical symptoms or laboratory findings that indicate an infection in a patient exposed to a medicinal product. This term applies only when a contamination of the study drug is suspected

There are no Ocrelizumab Events of Special Interest.

METHODS AND TIMING FOR ASSESSING AND RECORDING SAFETY VARIABLES

The investigator is responsible for ensuring that all AEs and SAEs that are observed or reported during the study, are collected and reported to the FDA, appropriate IRB(s), and Genentech, Inc. in accordance with CFR 312.32 (IND Safety Reports).

Adverse Event Reporting Period

The study period during which AEs and SAEs as described in Section 5.2 where the patient has been exposed to Genentech product must be reported. Reporting period begins after informed consent is obtained and initiation of study treatment and ends 24 weeks following the last administration of study treatment or study discontinuation/termination, whichever is earlier. After this period, investigators should only report SAEs that are attributed to prior study treatment.

Assessment of Adverse Events

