Complete physical examination ^h		x	x	x	x	x	x	x	x	x	x	x	x	x
EDSS		x	x		x	x	x	x	x	x	x	x	x	x
Neurologic examination ⁱ		x	x	x	x	x	x	x	x	x	x	x	x	x
Prescreen MRI	x ^w													
MRI brain ^{p,q}		x			x	x	x	x		x		x	x ^r	x ^r
MRI C-spine ^{p,q}		x			x	x	x	x		x		x	x ^r	x ^r
Symbol Digit Modality test for cognition	x*		x		x	x	x	x	x	x	x	x	x	x
Neuro QoL	x*		x		x	x	x	x	x	x	x	x	x	x
Assessment of neurologic event			x	x	x	x	x	x	x	x	x	x	x	x
Hematology, chemistry, and urinalysis ^j (Local lab)		x	x	x	x	x		x		x	x	x	x	x
Pregnancy test ^k		x	x	x	x	x								x
Hepatitis screening		x												
Hepatitis B virus DNA test ^l		x												

	Pre-screening (family members)	Screening ^a	Double-Blind Phase ^v											Unscheduled Visit ^b	Study Completion/ Early Termination ^c
Week	-6	-6	0 Baseline	2	24	48	72	104	130	156	182	208			
Visit Windows (days)	-45-1	-45-1	(-28)	(± 7)	(± 7)	(± 7)	(± 7)	(± 7)	(± 7)	(± 7)	(± 7)	(± 7)			
Quantitative Ig (total Ig, IgG, IgM, and IgA) (local lab)		x													
Quantitative Ig (total Ig, IgG, IgM, and IgA) (central lab)			x ^x		x	x	x	x	x	x	x	x	x	x	x
Lumbar puncture/CSF analysis (local lab and biomarkers) ^{m,p,s}			x ^x					x					x	x ^t	x ^r
Peripheral blood sample for biomarkers ^{m,s,t}	x		x ^x		x	x	x	x	x	x	x	x	x	x	x
Peripheral blood sample, paired with CSF			x ^y					x ^y				x ^y	x ^y	x ^y	
Serum samples for biomarkers ^{m,s}	x		x ^x		x	x	x	x	x	x	x	x	x	x	x
Gingival swab for storage	x [*]		x ^x		x	x	x	x	x	x	x	x	x	x	x
Adverse events ^u		x	x	x	x	x	x	x	x	x	x	x	x	x	x
Concomitant medications review		x	x	x	x	x	x	x	x	x	x	x	x	x	x
Randomization IxRS		x													
Methylprednisolone and antihistamine premedication ⁿ			x	x	x	x									
Ocrelizumab or placebo administration ^o			x	x	x	x									

eCRF = electronic Case Report Form; EDSS = Expanded Disability Status Scale; HBcAb = hepatitis B core antibody; HBsAg = hepatitis B surface antigen; HBV = hepatitis B virus; HepCAb = hepatitis C; MRI = magnetic resonance imaging; MS = multiple sclerosis; NfL = neurofilament light; WGS=Whole genome sequencing; PBMC=peripheral blood mononuclear cells; CSF= cerebrospinal fluid.

Note: (x) indicates that an assessment will only be done if needed.

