ⁱ Neurological examinations will be used to distinguish a neurologic event suggestive of MS (i.e., CNS demyelination) from other neurological (non-MS) disorders. Potential neurologic events suggestive of CNS demyelination should be recorded throughout the study period. Investigators will also screen patients for signs and symptoms of worsening neurologic function localized to the cerebral cortex, such as cortical symptoms/signs, behavioral and neuropsychological alteration, retrochiasmal visual defects, hemiparesis, cerebellar symptoms/signs (e.g., gait abnormalities, limb incoordination). Patients with suspected PML should be withheld from ocrelizumab treatment until PML is ruled out by complete clinical evaluation and appropriate diagnostic testing. A patient with confirmed PML should be withdrawn from the study. PML should be reported as a serious adverse event (with all available information) with immediate notification of the Medical Monitor.

^j Hematology will include hemoglobin, hematocrit, RBCs, WBC absolute and differential, absolute neutrophil count, and quantitative platelet count. Chemistry will include AST, ALT, total bilirubin, urea or BUN, creatinine, potassium, sodium and calcium. Standard urinalysis will be used to assess kidney function. For those patients enrolled with negative HBsAg and positive total HBcAb, HBV DNA (PCR) must be repeated every 24 weeks during these timepoints.

^k Serum or urine β -hCG must be performed at screening in women of childbearing potential within 14 days prior to initiation of study drug. Subsequently, urine β -hCG (sensitivity \geq 25 mIU/mL) must be collected. On infusion visits, the urine pregnancy test should be performed prior to premedication in all women of childbearing potential. If positive, ocrelizumab should be withheld and pregnancy status confirmed with serum β -hCG test.

^l All patients must have negative HBsAg result and negative HepCAb screening tests prior to study enrollment. If HBcAb is positive at screening, HBV DNA measured by PCR must be negative. For those patients enrolled with negative HBsAg and positive total HBcAb, HBV DNA (PCR) must be repeated every 24 weeks during the treatment period.

^m Biomarkers assessed in peripheral blood, CSF, and serum include adaptive and innate immune cell subsets and their soluble factors, RNA, DNA, genetic risk factors (e.g. HLA-DRB1*15:0), and other emerging exploratory markers of disease biology as appropriate. If samples are

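### No liver chemistry is scheduled between the last infusion at Week 48 and Week 104, and the HBV DNA repeat rule cannot be kept at the visits the schedule marks

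*Combined protocol and SAP*

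**What the plan says.** The last study drug infusion is at Week 48. Appendix 1 marks the local "Hematology, chemistry, and urinalysis" row at Screening, Weeks 0, 2, 24, 48, 104, 156, 182 and 208, and at unscheduled and completion or early termination visits. Weeks 72 and 130 are blank. Of the planned safety tests, only this row carries AST, ALT, total bilirubin, hemoglobin and platelets.

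The Laboratory, Biomarker, and Other Biological Samples section states: "Pre-infusion laboratory test results need to be available for review before each infusion, unless otherwise specified". The Hepatitis Screening and Liver Function Monitoring section states: "Liver function (i.e., ALT, AST, alkaline phosphatase, and total bilirubin) should be reviewed throughout the study". The Adverse Events of Special Interest section lists: "Cases of potential drug-induced liver injury that include an elevated ALT or AST in combination with either an elevated bilirubin or clinical jaundice". The Adverse Event Reporting Period section closes routine reporting 24 weeks after the last administration, or at study discontinuation if that is earlier. Footnote u of Appendix 1 has adverse events reported throughout the study.

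Patients with past resolved hepatitis B (HBcAb positive, viral DNA negative) may enroll and "will have the hepatitis B viral DNA checked regularly as per the schedule of activities". In that schedule the HBV DNA row is marked at Screening only, and two footnotes carry the repeat rule:
- Footnote j, on the hematology and chemistry row: "HBV DNA (PCR) must be repeated every 24 weeks during these timepoints".
- Footnote l, on the HBV DNA row: "HBV DNA (PCR) must be repeated every 24 weeks during the treatment period".

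Footnote l does not define the treatment period. The Prohibited Therapy section describes the treatment portion as running through Week 72.

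**The concern.** The Week 48 panel is taken before the dose, so it cannot show anything that dose does. With Week 72 blank, an asymptomatic rise in transaminases or bilirubin after the third course has no scheduled test to reveal it until Week 104. Both limbs of the Hy's-law definition need an ALT or AST value, so the schedule gives little chance of finding this event of special interest in the period when adverse events are formally collected. The planned laboratory summaries by arm (Safety Analyses section) would also have no scheduled hepatic or full local blood count values in either arm over that interval.

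For HBcAb-positive patients, the text sends sites to a schedule whose grid shows no repeat test and whose footnotes imply different durations. Sites could reasonably test at different visits. A confirmed positive result matters even when no dose remains to be withheld, because the protocol then asks for immediate referral to a hepatologist.

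**Working it through.** **Reading the row.** The schedule has 14 columns and the row has 14 cells. Complete rows such as physical examination, EDSS and SDMT line up the same way, so the blank cells are not an effect of text extraction.

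| Column | Local panel |
|---|---|
| Pre-screening | blank |
| Screening, Weeks 0, 2, 24, 48 | marked |
| Week 72 | blank |
| Week 104 | marked |
| Week 130 | blank |
| Weeks 156, 182, 208 | marked |
| Unscheduled, completion or early termination | marked |

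**Intervals between scheduled local panels, in weeks.**
- 2 − 0 = 2; 24 − 2 = 22; 48 − 24 = 24
- 104 − 48 = 56; 156 − 104 = 52; 182 − 156 = 26; 208 − 182 = 26
- With ±7 days at each visit, the 56-week gap ranges from 54 to 58.

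**Adverse event reporting window.** For a patient given all three courses it ends at 48 + 24 = Week 72. Scheduled chemistry draws after the Week 48 infusion and up to Week 72: none.

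**HBV DNA under each footnote.**
- Footnote j, using marked hematology visits at least 24 weeks apart: Weeks 24, 48, 104, 156, 182 and 208, which is 6 tests. The gaps are 24, 56, 52, 26 and 26 weeks. The 26-week gaps can shrink to 24 within the visit windows (26 − 2 = 24). The other two cannot (56 − 2 = 54; 52 − 2 = 50).
- Footnote l, if the treatment period ends with the Week 48 infusion: Weeks 24 and 48, which is 2 tests.
- Footnote l, if it ends at Week 72: Weeks 24, 48 and 72, which is 3 tests. The Week 72 test is not on footnote j's list.
- On either reading, footnote l stops by Week 72 while footnote j's visits continue to Week 208.

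**Drug effect over the same period.** The Delayed Return of Peripheral B Cells section reports repletion at a median of 72 weeks after the last infusion, range 27 to 175, in 51 patients. In study weeks: earliest 48 + 27 = 75, median 48 + 72 = 120, latest 48 + 175 = 223. Week 72 therefore precedes the earliest repletion seen.

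**After the change.**
- Chemistry with Week 72 added: the 56-week gap becomes 72 − 48 = 24 and 104 − 72 = 32. The gap of 52 weeks from Week 104 to Week 156 stays.
- HBV DNA at Weeks 24, 48, 72, 104, 130, 156, 182 and 208: 8 tests, gaps 24, 24, 32, 26, 26, 26 and 26, largest 32. That is 8 − 6 = 2 more tests than footnote j's visits give.

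**The case against.** The strongest reply is that panel frequency is a design choice. Local laboratory values serve to clear a patient for dosing, and no dose follows Week 48. The instruction on reviewing liver function sets no interval, and panels continue to Week 208. Hepatotoxicity is not among the listed ocrelizumab risks, and no HBV reactivation was reported in MS interventional studies. All of this stands and limits the weight of the point.

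A reader might infer that patients are unmonitored at Week 72. The documents do not support that. Physical examination, adverse event review, concomitant medication review, central immunoglobulins and blood biomarker samples are all marked there. The central cell-subset panel includes neutrophils, and critical blinded results trigger reflex messages to investigators. One Hy's-law limb rests on jaundice, which could prompt an unscheduled visit. The gap therefore concerns asymptomatic change in liver tests, hemoglobin and platelets.

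A reader might also infer that the two footnotes contradict each other outright. They agree on the population, the interval, and Weeks 24 and 48. They differ in duration, and doing both satisfies both. The difference at Week 72 arises only if footnote l's treatment period takes its end from the Prohibited Therapy section. Nor is it fair to count every nominal 24-week date as a missed test, because no visit exists at Weeks 96, 120, 144, 168 or 192.

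Lastly, slow B-cell repletion might be taken as a sign of continuing liver risk. Nothing in the documents links it to ALT, bilirubin, hemoglobin or platelets. It shows only that the drug's B-cell effect lasts through the gap.

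**Conclusion.** The point holds and should be corrected. After the last course, liver chemistry and a full local blood count are not scheduled for 56 weeks, and then not for a further 52. No scheduled chemistry falls inside the adverse event reporting period that follows the last infusion. Separately, a mandatory 24-week HBV DNA repeat cannot be kept at the visits footnote j points to after Week 48, and footnote l limits the repeat to a period it leaves undefined.

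The figures assume that a patient receives all three courses on schedule, that Week 48 samples are drawn before the infusion, and that no unscheduled or early termination visit intervenes. The number of HBcAb-positive patients is not given, so the reach of the HBV part cannot be sized. No efficacy endpoint is affected, and a Week 72 result would not change dosing. Its value lies in detecting post-treatment abnormalities and in a usable laboratory comparison between arms.

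**What to change.** 1. Mark local chemistry (AST, ALT, total bilirubin) at Week 72, using the visit and blood draw already planned. This draw falls at the end of the reporting window, 22 to 26 weeks after the infusion once both ±7-day windows are allowed for. State that an abnormality found there is to be reported.
2. If hematology is added at Week 72 as well, settle first how the lymphocyte result is handled. The Blinding section lists the lymphocyte count among results to be blinded, yet the local differential reports it. Chemistry alone answers the liver concern.
3. Mark the HBV DNA row (x), the grid's sign for an assessment done only if needed, for HBsAg-negative, HBcAb-positive patients at Weeks 24, 48, 72, 104, 130, 156, 182 and 208. Have footnotes j and l both cite this list as the working form of the 24-week rule.
4. Consider chemistry at Week 130 too, which would bring the largest interval between panels down to 32 weeks. Otherwise give a reason for keeping the 52-week gap.

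The cost of items 1 and 3 is about 100 extra local chemistry panels (one per patient) and, against footnote j's visits, HBV DNA tests at Weeks 72 and 130 for each HBcAb-positive patient. Against footnote l the addition is larger: 8 − 3 = 5 or 8 − 2 = 6 tests, depending on where the treatment period ends. Item 4 would add up to about another 100 panels. The HBV list still contains one 32-week interval, between Weeks 72 and 104; closing it would need a new visit.
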